4.5.1 Important Protocol Deviations Leading to Exclusion from the PPS Analysis

A protocol deviation (PD) is any change, divergence, or departure from the study design or procedures of a study protocol. A protocol deviation may be a reason to remove data from an analysis set at the time of analysis. PDs can be either observable or programmable. Programmable PDs are those PDs that can be programmed from the data recorded in the clinical database. Observable PDs are PDs identified by CRAs or other team members.

PDs will be classified as major and minor using a prespecified list of types of deviations. Major PDs are defined in accordance with ICH E3 as important PDs related to study inclusion or exclusion criteria, conduct of the trial, subject management or subject assessment resulting in the potential to jeopardize the safety or rights of the trial subjects or the scientific value of the trial.

All PDs will be evaluated before unblinding and most will be classified into the following categories:

- Subject randomized and did not satisfy entry criteria
- Subject received the wrong treatment or incorrect dose
- Subject took an excluded concomitant medication
- Key study procedures missed or performed out of window, such as, for immunogenicity if the serum sample was collected outside the time window of 21 days the subject did not comply with the blood draw schedule and will be excluded from the PPS population. Hence, subjects will be excluded from PPS if blood draws >21 days after any vaccination.

The impact of major PDs on the efficacy, immunogenicity and/or safety results will be investigated by assessing the robustness of the study results.

Major PDs will lead to exclusion of the subject or part of the subject's data from at least one analysis set.

The number of subjects in any and by PD category will be summarized by treatment group, center and overall. Individual subject listings will be provided in an appendix, sorted by subject and by PD category.

Prior to unblinding the analysis, designated Seqirus staff will develop a memo that describes the PDs that led to exclusions from analysis sets. This memo will be signed off by at least the Biostatistician and the Clinical Scientist and will be included in the trial master file (Exclusion Memo).

Prematurely terminating study participation for reasons such as withdrawal of consent or occurrence of AEs (including death) is not considered as a PD. Any missing assessments that should have otherwise been collected for that subject later in the study is also not considered as a PD.

Deviations from the protocol will be documented on an ongoing basis by the study monitors and lead clinical research associate or designee throughout the study period.

At the time of database lock, prior to unblinding and while the major PDs are being reviewed, the project manager or designee will forward all relevant documentation highlighting PDs to the study statistician. These deviations will be included in the protocol deviation document for agreement and will be listed with the PDs in the clinical study report (CSR).

. PD listings will be reviewed by Seqirus prior to the finalization of the population datasets, which will occur prior to unblinding. The list will be used to determine which subjects should be excluded from either the FAS or the PPS.

4.6 Special Subpopulations

Not Applicable.

5. DATA Handling

5.1 Time points and Visit Windows

A summary of the assessments required at each study visit is described in [\(Appendix A\)](#).

Day 1 is defined as the day of first dose of the vaccination.

Relative days after Day 1 are calculated as (assessment date – Day 1 date) + 1. Relative days prior to Day 1 are calculated as (assessment date – Day 1 date). The day prior to Day 1 is Day -1

The following visit windows will be used.

Table 5.1-1: Visit windows for previously vaccinated subjects

Statistical Analysis Plan

Sponsor Name: Seqirus
Sponsor Protocol ID: V130_10

Study part	Scheduled visit	Time interval (days)
Screening	Screening Visit	< 10 Days before Day 1
Treatment period	Clinic Visit V1	Day 1
	Reminder Phone V1	Day 3 (-1/+1 Day)
	Clinic Visit V2	Day 28 (+ 7 Days)
Follow-up Period	Safety Phone call V3	Day 90 (+ 7 Days)
	Safety Phone call V4	Day 180 (+ 14 Days)

Table 5.1-2: Visit windows for not previously vaccinated subjects

Study part	Scheduled visit	Time interval (days)
Screening	Screening Visit	< 10 Days before Day 1
Treatment period	Clinic Visit V1	Day 1
	Reminder Phone V1	Day 3 (-1/+1 Day)
	Clinic Visit V2	Day 28 (+ 7 Days)
	Reminder Phone	V2 + 2 Days (-1/+1 Day)
	Clinic Visit V3	V2 + 28 Days (+7 Days)
Follow-up Period	Safety Phone call V4	V2 + 90 Days (+7 Days)
	Safety Phone call V5	V2 + 180 Days (+14 Days)

Visit window deviations will be reviewed prior to unblinding.

5.2 Missing Values – Missing Visit.

Missing, unused and spurious data will be dealt with as such. There is no intention to implement any procedure for replacing missing data.

Titer values recorded as <1:10 (or < lower limit of quantification [LLOQ]) will be summarized as 1:5 (or ½* LLOQ).

No imputation of missing solicited or unsolicited AEs will be used but implausible measurement will be removed as described below. The percentage of subjects with missing solicited AE assessments (e.g. missing Patient Diary) and missing Safety Phone Calls or Safety Assessments will be reported for each time period.

Missing immunogenicity values are considered missing completely at random (MCAR) and therefore will not contain information that impact the result of the analysis (i.e., not informative). Imputation methods will therefore not be used.

The PPS will be used for the primary immunogenicity analysis and a supporting analysis will be performed using the FAS Immunogenicity, as noted in Section 4.4 FAS Immunogenicity.

Duplicate tables of primary and secondary immunogenicity analyses may also be produced based on the FAS Immunogenicity if there is >5% difference in the total number of subjects between the PPS and the FAS Immunogenicity.

Exclusions of Individual Values for Safety Analyses

Some local and systemic AEs will be directly measured by the subject and will not be subject to a reconciliation process, even if they are biologically implausible.

Therefore, these implausible measurements will be removed from the analysis but included in listings.

Implausible measurements are summarized in the table below:

Table 5.2-1: Implausible Solicited Adverse Events

Parameter	Implausible measurements
Body temperature	$\leq 33^{\circ}\text{C}$ or $\geq 42^{\circ}\text{C}$
Erythema Measurements	≥ 450 mm or < 0 mm
Induration Measurements	≥ 250 mm or < 0 mm
Ecchymosis Measurements	≥ 250 mm or < 0 mm

6. Statistical Methods

6.1 General Principles

All data processing, summarization and analyses will be performed using ██████'s SAS Environment / Version 9.3 (or later) of the SAS® statistical software package.

The FAS will be used for summaries of baseline characteristics and background data, analyses will be repeated on the All Enrolled Set and PPS; the Safety population will be used for all safety analyses; the PPS will be used for the primary and secondary analyses; and the FAS population will be used for supporting analysis of the primary endpoint, and all other immunogenicity endpoints.

Descriptive statistics will be used to present all safety and immunogenicity results: number of observations (n), mean, standard deviation (SD), median, minimum (min), maximum (max) for continuous data and frequency and percentage relative to the appropriate population for categorical data.

Binary data (ie, percentages of subjects with SCR) will be summarized for each group using unadjusted estimates and will be reported together with two-sided exact 95% Confidence Intervals (CIs) (Clopper-Pearson).

The difference between the proportions of treatment groups will be determined and the corresponding two-sided 95% CIs calculated by Miettinen-Nurminen method.

Geometric means and 95% CIs will be calculated by taking the anti-logs of the means and 95% CI of the log transformed immunogenicity parameters. Exact CIs based upon the binomial distribution will be calculated for percentages.

Statistics will be displayed for the following:

- Seqirus QIVc
- Comparator QIV
- Overall

In the summary tables, the strains will be displayed as follows:

- Cell antigen:

- H1N1: A/Idaho/07/2018
- H3N2: A/Indiana/08/2018
- B-yam: B/Singapore/INFTT-16-0610/2016
- B-vic: B/Iowa/06/2017
- Egg antigen:
 - H1N1: A/Brisbane/02/2018 (IVR-190)
 - H3N2: A/Kansas/14/2017 (X-327)
 - B-yam: B/Phuket/3073/2013 (BVR-1B)
 - Bvic: B/Maryland/15/2016

All data will be listed.

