Enrolled subjects will be randomized in the Interactive Response Technology (IRT) system by a 2:1 ratio and automatically assigned a unique Subject ID. Subjects participating in the CMI subset (approximately 84 subjects) will be enrolled in a limited number of sites through sequential allocation. The Subject ID will be the subject's unique identification number for all eCRFs and associated study documentation that will be used for duration of the study. After randomization, the Screening Number ceases to be used and remains in the Screening and Enrolment Log only. The list of randomization assignments is produced by the EDC/IRT service provider and approved by Seqirus according to applicable Seqirus Standard Operating Procedure (SOP).

Stratification through IRT will be used to ensure a balanced distribution among the age groups, at least 30% of the subjects should be 6 through 23 months and at least 30% of the subjects should be from 24 through 47 months of age.

For A/H1N1, B/Victoria, and B/Yamagata strains, immunogenicity of QIVc and US-licensed QIV will be evaluated by MN assay in a 20% subset of subjects. After blood specimens have been collected a randomly selected subset (20%) of these samples will be analyzed.

If for any reason, after signing the Informed Consent Form (ICF), the subject who is eligible and enrolled fails to be randomized, this is called a randomization failure. The reason for all randomization failures will be recorded in the Screening and Enrollment Log.

If for any reason, after randomization the subject fails to undergo treatment, this is an Early Termination and the reason should be recorded in source document.

The information on these Early Termination subjects should be kept distinct in the source documentation from randomization failures.

Blinding

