2.3 Sample Size and Power

Seqirus QIVc will be tested against comparator, i.e. US-licensed comparator QIV. The treatment randomization ratio is 2:1 (Seqirus QIVc: Comparator QIV).

This study is designed to achieve at least 90% power to demonstrate noninferiority for all of the 8 endpoints: seroconversion rates for 4 strains and Geometric Mean Titers (GMTs) for 4 strains using a one-sided alpha of 0.025 for each comparison. No alpha adjustment for multiple endpoints will be made. For comparisons of Seroconversion rate (SCR) a noninferiority margin of 10% (Comparator QIV-Seqirus QIVc) will be employed. It is assumed that the SCRs for A/H1N1, B strains and A/H3N2 based on Cell-based Trivalent Influenza Vaccine (TIVc) are 81%, 69% and 85% respectively. These estimates are based on the estimated SCR rates of historical data, namely from study *V58P16*.

It is also assumed that the expected difference between antibody titers (QIV minus QIVc) is consistent with the SCR differences reported as per *V58P16*, namely 7% for A/H1N1 and 5% for A/H3N2 (based on the MN assay).

It is assumed that there is no difference between Seqirus QIVc and the comparator QIV for the B/strain.

For comparison of GMT ratio, a noninferiority margin of 1.5 (Comparator QIV/ Seqirus QIVc, equivalent to a difference on the log scale of 0.405465108) will be employed for the assessment for the A/H1N1, A/H3N2 and B strains. It is assumed that the GMT ratios for A/H1N1, A/H3N2 and B strains for QIVc are 1.49 for the A/H1N1, 1.00 for the A/H3N2 (based on the MN assay) and 0.84 for the B-strains. These GMT ratio estimates are consistent to those observed from protocol *V58P16*. It is assumed that the standard deviation of $\log_e(\text{titer})$ is 1.3 across all strains.

Under these assumptions and with n evaluable = 1450 in the Seqirus QIVc group and 725 in the Comparator QIV the power for 4 GMT ratio endpoints is 94.90% and the power for 4 SCR endpoints is 99.40%. The overall global power of the 8 endpoints is then $94.9\% \times 99.4\% = 94.33\%$.

This provides a total N evaluable = 2175. Allowing for a 10% drop-out, 2418 subjects will be recruited for immunogenicity assessment. Approximately 84 additional subjects between 24 through 47 months of age will be enrolled to study CMI

Statistical Analysis Plan

Sponsor Name: Seqirus
Sponsor Protocol ID: V130_10

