6.5.1.3 Statistical Methods

All statistical analyses for HAI (or MN) titers will be performed on the logarithmically transformed (base 10) values. Individual HAI titers below the detection limit (<10) will be set to half of that limit (5). Individual MN titers below the LLOQ, will be set to half of that limit ($1/2 * \text{LLOQ}$).

Co-primary immunogenicity endpoints of GMT and SCR for each virus strain contained in the vaccine will be assessed in subjects 6 Months through 47 Months of Age overall.

Statistical Analysis Plan

Sponsor Name: Seqirus
Sponsor Protocol ID: V130_10

Primary analysis will be performed in subjects 6 Months through 47 Months of Age for the Per-Protocol Set. The difference in SCRs will be presented with exact 95% CIs. Each of the four strains will be analyzed separately.

For immunogenicity data, the immunogenicity analysis will comprise a complete case analysis only, without introducing any bias. Imputation methods will not be used.

To determine the GMT ratio (adjusted analysis) a general linear model (GLM) will be fitted on log transformed (base ten) post-vaccination HAI (or MN) titer as the outcome variable and terms for covariates: vaccine treatment, pre-vaccination HAI (or MN) titer, age stratum, gender, vaccination history, age-by-vaccine interaction and study site. Potential covariate interaction effects will also be examined in the fit of the GLM. From the model, an adjusted difference in least square means (on the log scale) will be produced with 95% confidence limits. The estimated difference and the confidence limits will be back transformed to obtain an *adjusted GMT ratio* with 95% confidence limits. Each of the four strains will be analyzed separately. The adjusted GMT ratio will be the result for which the non-inferiority assessment of the HAI (or MN) GMT co-primary endpoint will be based on.

The statistical models might be reduced in case they fail to converge.

The complete set of covariates that will be used in the model to calculate the adjusted GMT ratio will include treatment group (2 treatments), pre-vaccination GMT titer (value), age strata (2 categories, 6 through 23 months or 24 through 47 months), gender (male or female), influenza vaccination received prior year (Yes or No), and investigator site (site identifier).

The GLM specification is:

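### The four seroconversion co-primary tests use a crude difference although randomization is stratified by age; an age-stratified interval costs almost nothing and is narrower if seroconversion differs by age

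*SAP*

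**What the plan says.** **Design.** SAP 2.2 (Randomization) states: "Stratification through IRT will be used to ensure a balanced distribution among the age groups". The groups are 6-23 and 24-47 months, each to hold at least 30% of subjects. Protocol 5.1.4 says the same, and Protocol 5.1.3 has stratification information entered into the IRT at enrollment.

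**GMT half of the success rule.** The linear model in SAP 6.5.1.3 contains age stratum, gender, vaccination history, baseline titer and site, plus an age-by-vaccine term that is dropped if not significant.

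**SCR half.** Under SAP 6.1, binary data "will be summarized for each group using unadjusted estimates". The same section gives the interval for the comparison: "The difference between the proportions of treatment groups will be determined and the corresponding two-sided 95% CIs calculated by Miettinen-Nurminen method". SAP 6.5.1.3 has: "The difference in SCRs will be presented with exact 95% CIs". SAP 6.5.1.1 defines the criterion as the plain difference of the two group rates. None of these places names strata, weights or covariates. SCR by age appears only as a subgroup analysis (SAP 6.5.4). Appendix B has a heading for Miettinen-Nurminen code, but the code is redacted.

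**Success.** All eight co-primary tests must pass (SAP 6.5.1.1).

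**The concern.** When allocation is stratified by a factor that predicts the outcome, the treatment contrast is largely free of variation between strata. The crude two-sample variance p(1-p) still counts that variation. The interval set against the 10-point margin can then be wider than it needs to be.

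The analysis set adds a second reason. The primary analysis uses complete cases in the Per Protocol Set (SAP 4.5 and 6.5.1.3). Stratified allocation protects the age mix at randomization, not after exclusions. A stratified estimate corrects for a shift in age mix between arms, and a crude one does not.

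The two halves of one success rule also treat the same design factor differently. What is at stake is some precision and robustness in four of the eight deciding tests.

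**Working it through.** **Inputs (SAP 2.3 and Table 2.3-1).** The test level is set by "using a one-sided alpha of 0.025 for each comparison". For SCR, "a noninferiority margin of 10% (Comparator QIV-Seqirus QIVc) will be employed". The assumed SCRs for A/H1N1, the B strains and A/H3N2 "are 81%, 69% and 85% respectively". For the B strains: "It is assumed that there is no difference between Seqirus QIVc and the comparator QIV for the B/strain". Evaluable numbers are 1450 QIVc and 725 QIV.

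**Step 1: reproduce the plan's figure.** For the B strains:
- SE = sqrt[0.69 × 0.31 × (1/725 + 1/1450)] = sqrt(0.2139 × 0.002069) = 0.02104.
- Half-width = 1.96 × 0.02104 = 4.12 points.
- Power = Φ(0.10/0.02104 − 1.96) = Φ(2.794) = 99.74%. The plan states 99.7%.
- Two B strains with the rounded value: 0.997² = 99.40%, as stated.

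The plan's SCR power is therefore that of a crude comparison.

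**Step 2: stratified variance.** Let w be the share aged 6-23 months and d the SCR gap between age strata, with 2:1 allocation within each stratum. The within-stratum variance Σ w_k p_k(1−p_k) replaces p(1−p), and it equals p(1−p) − w(1−w)d². For w = 0.5 and d = 0.20: 0.2139 − 0.25 × 0.04 = 0.2039. The ratio is 0.953, its square root 0.976, and the half-width 0.976 × 4.12 = 4.03.

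The gap d is an assumption, because the documents give no SCR by age. The share w is taken as 0.3 and 0.5, since the SAP allows 30% to 70%.

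| Assumed gap (points) | Half-width, B strains | Narrower by | Power at zero difference |
|---|---|---|---|
| 0 | 4.12 | 0% | 99.74% |
| 10 | 4.10 | 0.5-0.6% | 99.76% |
| 20 | 4.03-4.04 | 2.0-2.4% | 99.81-99.82% |
| 30 | 3.90-3.94 | 4.5-5.4% | 99.87-99.89% |
| 40 | 3.72-3.79 | 8-10% | 99.94-99.95% |

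For the A strains at a 20-point gap, the half-width goes from 3.50 to 3.38-3.40 (A/H1N1) and from 3.18 to 3.06-3.08 (A/H3N2). With a true difference of zero, power stays at about 100%.

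**Step 3: all eight endpoints.** The four GMT tests reproduce at 94.93%. Then 0.9493 × 0.99739² = 94.4%, and at the largest gap 0.9493 × 0.99954² = 94.8%. The rise is about 0.4 point, because the B-strain GMT tests limit the total.

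**Step 4: validity of the crude test.** Under stratified allocation its actual one-sided level is Φ(−1.96 × SE_crude/SE_strat). For w = 0.5:
- 20-point gap: Φ(−1.96/0.976) = 2.2%.
- 40-point gap: Φ(−1.96/0.902) = 1.5%.

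Both are below 2.5%. Simulated Miettinen-Nurminen intervals (1500 runs per scenario, simulation error about 0.6 point) agree. Crude coverage was 94-96% for gaps of 0-20 points and about 97% at 40, against about 95% stratified.

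**Step 5: nearer the margin.** Suppose QIVc is truly 5 points lower, with the 69% variance kept in both arms. Crude power is Φ[(0.05 − 1.96 × SE_crude)/SE_strat] and stratified power is Φ(0.05/SE_strat − 1.96).
- 20-point gap: 66-67% crude, 68% stratified.
- 40-point gap: about 68% crude, 73-75% stratified.

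**Step 6: imbalance after exclusions.** If the Per Protocol arms differ by 3 points in age mix and SCR differs by 20 points between strata (both assumed), the crude difference shifts by 0.03 × 20 = 0.6 point. Stratification removes this.

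**The case against.** The strongest case against is that the planned analysis is sound. It does not inflate type I error, its stated power reproduces, and the gain depends on a figure that the documents lack. At gaps of 10-20 points the interval narrows by only 0.5-2.4%. All of this stands, and it limits the point to efficiency and consistency.

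Four further arguments:
- **The GMT and SCR endpoints differ in kind.** SCR already uses each child's baseline titer by definition, so a leaner SCR analysis is not an error. That is true, but age stratum is a design factor, and baseline titer does not stand in for it.
- **The IRT wording could describe an enrollment quota.** Protocol 5.1.3 and the term stratification point to true strata. If it were only a quota, the crude test would not be conservative, but stratifying would still gain similar precision.
- **The redacted code may contain a strata option.** This cannot be excluded. The text should say so in any case.
- **SCR by age is already planned.** Subgroup results do not enter the deciding test.

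A reader might also infer that vaccination history belongs among the strata because the GMT model includes it. The documents do not support that by the same argument. It is not a stated randomization factor. It is also defined in two ways: at least two prior doses in the Protocol definitions, but vaccination in the prior year in SAP 6.5.1.3. No gain from a four-cell stratification has been calculated here.

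**Conclusion.** The point holds as a low-cost improvement. The text gives the SCR difference no stratification, although age is a randomization stratum and the GMT tests adjust for it. If SCR differs by age, the crude interval is wider than necessary: by nothing at no gap, by about 2% at 20 points and by 8-10% at 40 points for the B strains. Age imbalance after exclusions is also left uncorrected.

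A reader might infer that the SCR tests are invalid, or that the trial is underpowered for lack of stratification. Neither follows. The crude test is valid to slightly conservative, and the plan's 99.7% per B strain was computed for it. Stratifying adds about 0.2 point per B strain at most. Even that slightly overstates the gain: under stratified allocation with a 40-point gap, the crude test itself has power Φ(2.794/0.902) = 99.90%.

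The conclusion rests on the assumed gaps, an overall SCR of 69%, 1450 and 725 evaluable children, and a 30% or 50% share in the younger stratum. The benefit matters mainly if the true difference is nearer the margin than planned.

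**What to change.** Before unblinding, state in SAP 6.1 and 6.5.1.3 that SCR noninferiority for each strain is judged on the upper limit of a two-sided 95% Miettinen-Nurminen interval for QIV minus QIVc, stratified by age stratum as randomized, with Mantel-Haenszel weights. Report the crude difference and its interval as supportive. Replace the reference to exact intervals in 6.5.1.3 in the same edit, so that one method decides.

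The cost is one sentence in the SAP and one line of code. If the strata do not differ, essentially nothing is lost. The small downside is that the stratified difference will not exactly equal the subtraction of the two crude percentages, so the tables need a footnote.
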